### **Participant retention strategies.**

Participants will complete a "contact form" including basic information, i.e., name, address, phone number, email. Participants in the GP or IP arms who miss  $>$  three consecutive behavioral sessions will be contacted by phone, text or email (maximum of three attempts). A maximum of three attempts will also be made to contact participants in the EUC arm who do not attend a scheduled session.

### **Outcome assessments.**

Outcomes will be obtained at each participating clinic. As outlined in Table 3, most outcomes will be assessed at 0, 6, 12, and 18 months. Physical measures, i.e., height, weight, waist circumference, and blood pressure, will be obtained between 7-11 a.m., following a minimum 12-hour fast, by trained research assistants blinded to condition. Research assistants will receive refresher training and complete reliability assessments for physical measures two to three times each year.

**Anthropometric measures.** Weight will be measured with a digital scale accurate to  $\pm 0.1 \text{ kg}$  (Befour Inc. #PS6600, Saukville, WI) with participants in a hospital gown. Height will be measured with a stadiometer (Model #IP0955, Invicta Plastics Limited, Leicester, UK). The average of two measures within 0.25 cm will be recorded. Body mass index (BMI) will be

calculated as weight (kg) divided by height ( $m^2$ ). Waist circumference will be measured with an anthropometric tape using the procedures described by Lohman et. al. (72). Three measurements will be obtained with the outcome recorded as the average of the closest 2 measures.

**Blood chemistry/ blood pressure.** Fasting blood samples will be obtained by a clinic phlebotomist. Analysis of HDL and LDL cholesterol, triglycerides, glucose, and HbA1c (diabetics) will be completed by the commercial laboratories that are contracted by each participating clinic. Blood pressure will be obtained in duplicate, with an automated sphygmomanometer (DinaMap ProCare 100, General Electric Healthcare, Chicago, IL) using the National Health and Nutrition Examination Survey (NHANES) blood pressure protocol (73).

**Compliance with diet recommendations.** Energy and macronutrient intake will be assessed using the self-administered, web-based VioScreen Graphical Food Frequency System (Viocare Technologies, Inc., Princeton, NJ). Participants will complete the survey at a computer in a private room during the clinic assessment visit, or at home on a tablet or personal computer within one or two days following the clinic visit. Participants who fail to complete the survey within that time frame will receive email and telephone reminders. Assessment of nutrient intake using VioScreen is correlated with assessments obtained from a traditional paper and pencil food frequency questionnaire: total fat = 0.82, saturated fat = 0.84, protein = 0.67, carbohydrate = 0.79, alcohol = 0.90 (74).

**Compliance with physical activity recommendations.** Participants will wear an ActiGraph Model GT3X+ (ActiGraph LLC, Pensacola, FL) portable tri-axial accelerometer on a belt over the non-dominant hip, at the anterior axillary line, during waking hours for seven consecutive days, with the exception of bathing, swimming and contact sports. The ActiGraph accelerometer has been shown to provide valid and reliable assessments of PA in adults (75-77). A 7-day monitoring period provides a reliable estimate of moderate-to-vigorous PA (78-80). ActiGraphs will be initialized and downloaded using ActiLife Software version 6.13.3 or higher and set to collect in the raw data mode at 60 Hz. ActiGraph data will be processed using the protocol used for adults in the 2003-2004 and 2005-2006 cycles of NHANES (81, 82). Data will be aggregated over 60-sec epochs. The following intensity cut-points will be used: sedentary (< 1.0 METs;  $\leq$  100 counts/min), light (1.1-2.99 METs; 101-2019 counts/min.), moderate (3.0-5.99 METs; 2020-5998 counts/min) and vigorous  $\geq$  6 METs;  $\geq$  5999 counts/min) (81, 82). Non-wear time will be defined as at least 60 consecutive minutes of zero counts, with allowance for 1-2 min. of counts between 0 and 100. Counts  $\geq$  20,000/min will be considered spurious and will be deleted (83). We have a custom SAS program to complete these analyses. ActiGraphs, with instructions on their use, will be distributed to participants at their scheduled assessment visit clinic. Participants will be asked to wear the ActiGraph for seven consecutive days, beginning the day following the clinic visit, and return the ActiGraph to the research team using a postage pre-paid padded envelope provided.

**Questionnaires.** The following instruments will be used to assess behavioral factors that may impact weight management: Health Related Quality of life (HRQOL) will be assessed using the Short Form 36 (SF36) (84). Daily stress associated with eating, i.e., planning/preparing, monitoring nutrients, concerns about eating correctly, will be assessed with the Nutrition Hassles Questionnaire (85). Finally, the implementation of Social Cognitive Theory will be assessed by measuring the “active” ingredient, self-efficacy, using the Weight Efficacy Lifestyle Scale (WELS) (86), Barriers Self Efficacy (BARSE) (87), and the Exercise Self-Efficacy Scale (EXSE) (88). Acceptable construct validity and internal consistency of these instruments have been established (84, 85, 87-90). Questionnaires will be completed online using REDCap

software during the clinic visit by participants with no home internet access or at home within one or two days following the clinic visit for participants with home internet access.

### **Process evaluation**

As described below, process evaluation will monitor the fidelity of intervention delivery, the extent to which the intervention was implemented and received, and the extent to which participants actively engaged in the intervention across time.

**Intervention fidelity.** To assure quality control and standardization of intervention delivery, all GP, IP, and EUC sessions will be audio recorded. Research staff will randomly review one session each month in the GP and IP arms, and 25% of sessions in the EUC arm for each health educator. Recordings will be compared with a standardized checklist of specific content and time scheduled for delivery of that content. Health educators who fail to deliver at least 80% of scheduled content for the scheduled duration will be required to receive additional training from the research team that will be delivered remotely via FaceTime®. Health educators who fail to satisfy the intervention delivery criteria after receiving additional training will be replaced by another clinic staff member or a qualified community professional. A member of the research team will be available to substitute for health educators who are unable to deliver a session, or while a new health educator is trained in the event a health educator is dismissed or leaves the clinic. Health educator absences and turnover will be tracked and the effect on weight change will be evaluated in the analysis.

**Implementation.** The extent to which the intervention was implemented and received will be assessed using records of participant attendance at scheduled sessions that will be maintained by health educators.

**Engagement.** In addition to attendance, which will be tracked by health educators in all three intervention arms, participant engagement in the GP and IP arms will be estimated by participant compliance with the self-monitoring protocol, i.e., the frequency of reporting body weight, diet (portion controlled entrées, low calorie shakes, fruits and vegetables) and PA (pedometer steps, activity minutes).

**Structured interviews.** A convenience sample of 20% of participants, stratified by intervention arm, and a sample of clinic staff, e.g., health educators, physicians etc., will be invited to participate in structured interviews at both 6 and 18 months. Interviews will be conducted by phone and will be designed to gather information that might be useful in improving the interventions, and/or implementing the interventions in rural clinics. Topics will include, preference for intervention format, length, difficulties in complying with intervention components, suggestions for improving the intervention, overall satisfaction with the intervention, including the diet and PA recommendations, behavior session frequency, duration and content, and health educator performance. Information regarding resource use associated with participating and delivering the intervention for inclusion in the cost analysis will also be collected.

### **Cost considerations**

A potential advantage of remote delivery of weight management, e.g., GP or IP calls may be lower fixed and variable costs for both participants and providers. Fixed costs are independent of the number of participants while variable costs are directly associated with the number of participants enrolled (91). A process flow chart will be created and validated by consensus of the research team to assure a complete accounting of resources used in all intervention groups (92). Cost, cost effectiveness, and contingent valuation analyses will be completed at both 6 and 18 mos. as these costs may differ between the weight loss and weight maintenance phases of the interventions. The cost perspective for all analyses will be societal which includes the

value of participant time, as this time cannot be used for work or leisure. Both provider and participant costs will be collected prospectively.

**Provider costs.** The cost of space to conduct sessions with participants in the EUC arm, and to deliver both the GP and IP arms, will be estimated by multiplying the local market values for office per square foot by the amount of space utilized. Monthly billing statements will provide an estimate of utility costs including heat, electric, computer and internet services. The cost of provider time, i.e. wages and benefits, will be estimated as the number of hours worked obtained from provider maintained logs, multiplied by the provider's wage. Cost associated with purchase and shipping of the low calorie shakes provided to participants in both the GP and IP arms will also be tracked with billing and expense records.

**Participant costs.** The cost of participant time required to attend GP or IP sessions, or travel to and attend in-person sessions required in the EUC arm, will be estimated from self-reports of time spent in these activities multiplied by the median wage in the region. Transportation costs will be estimated from self-reported driving mileage multiplied by the federal mileage reimbursement rate.

**Cost analysis.** Differences in total costs and cost effectiveness; i.e., cost/kg weight loss between intervention arms will be evaluated using a one-way analysis of variance (ANOVA). We will also make qualitative comparison between the cost effectiveness of our interventions and others reported in the literature, such as the Diabetes Prevention Program (93). Weight loss represents only one potential benefit associated with participation in a weight management program. Other potential benefits included improved health, enhanced attractiveness, increased vitality and productivity etc. We will use contingent evaluation analysis where participants express preferences for hypothetical programs with different attributes such as costs, time, delivery method, and magnitude of weight loss to determine how differences in these affect preferences for the GP, IP and enhanced usual weight management strategies. Contingent valuation data will be analyzed using conditional logit analysis, with adjustments for clustering of observations within clinics.

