**Theoretical model.** The intervention will be grounded in Social Cognitive Theory, a triadic, dynamic model that indicates an individual's behavior is uniquely determined by the reciprocal interaction of personal, behavioral, and environmental factors, to effect change in energy intake (EI) and PA (54, 55). We will focus on social cognitive techniques which have been shown to be most effective for changing EI and PA including intention formation, goal setting, self-monitoring (diet, PA, weight), and participant feedback relative to intervention compliance (56). These techniques will be enhanced by employing behavior shaping (gradually modifying diet and PA), social support, and stimulus control (strategies to decrease cues for less desirable and increase cues for more desirable diet and PA behaviors). Additionally, cognitive strategies will be used to increase self-efficacy and to deal with social relationships affected by weight, such as identifying/confronting self-sabotage attempts, responding to stress with non-food techniques, relapse prevention strategies to teach participants to recognize precursors and consequences of lapses, and develop plans for addressing high risk situations. The intervention is also informed by both social ecologic (57) and social network theories (58) as content will be tailored to both the physical and social environment of participants.

**General Description.** All intervention arms will complete weight loss (6 mos.) and weight maintenance (12 mos.). Weight will also be evaluated following a 6 mos. no contact follow-up. A comparison of contact format and intervention session frequency and duration between intervention arms is shown in Table 2. The protocols for reducing EI, increasing PA, content presented during behavioral sessions, and self-monitoring diet, weight, and PA will be identical in the GP and IP arms. Participants in both the GP and IP arms will receive identical notebooks that will include detailed instructions for the weight loss and weight maintenance diets including recipes, instructions for PA, self-monitoring diet and PA, and the schedule for behavioral sessions. The notebooks will be organized by behavioral session and contain handouts, worksheets, and assignments specific to each session.

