**Group phone intervention: Delivery/session content.** The GP intervention will be delivered to 12-15 participants during a 45 minute call weekly from 0-6 mos. and biweekly from 7-18 mos. using the MaestroConference® software platform (Oakland, CA) that allows group audio conferences to be accessed by phone. Approximately five minutes prior to scheduled meetings, typically late afternoon or early evening, participants will call a toll-free line and enter a unique code number to join the meeting. Participants will be required to remain on the call for the duration of each session to be considered as having attended the session. Call duration for each participant is monitored by the Maestro software. Each meeting will include a check-in question to generate discussion regarding diet and PA, a review of participants self-monitored diet, weight and PA data reported since the previous meeting, a lesson on a weight management topic, and an experiential learning assignment requiring problem solving, or the practice of behavioral strategies, to be completed prior to the next meeting. Sample topics include: energy density (increase volume, not calories), obtaining fruits and vegetables in rural communities, exercising in rural communities, eating/exercising on the go, etc. Several sessions at the end of the weight loss phase (mo. 6) will include discussions regarding complying with a conventional diet, i.e., meal planning, food shopping, meal preparation, portion control, etc. During weight maintenance (7-18 mos.) group sessions will focus on planning and following a meal plan diet with or without incorporation of portion controlled entrées/shakes, and cardinal behaviors for successful weight maintenance such as self-monitoring, regular PA, eating on weekends/vacations, and controlling EI on special occasions and holidays, etc.

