**Individual phone intervention: Delivery/session content.** The IP intervention will be delivered via brief, i.e., ~15 min. scheduled phone calls weekly from 0-6 mos. and biweekly from 7-18 mos.. Prior to each call participants will be asked to read a lesson in the study notebook. Lesson topics will parallel those in the GP intervention and focus on weight loss over mos. 0-6 and weight maintenance during mos. 7-18. During each call, health educators will highlight the major points of the lesson, review self-monitoring data relative to weight, diet and PA, and problem solve, if necessary. Thus, the IP intervention is predominately self-directed with minimal education and support from the health educator. In contrast, the GP intervention includes health educator directed, 45 min educational/behavioral sessions, and provides both health educator and group support.

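### Phone-arm participant time is costed as session attendance only, so the lesson reading asked of IP participants before each call is left out and IP cost is probably understated relative to GP

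*Combined protocol and SAP*

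**What the plan says.** Under Cost considerations, the perspective is societal and includes the "value of participant time, as this time cannot be used for work or leisure". The Participant costs paragraph then lists what is counted: "The cost of participant time required to attend GP or IP sessions", or, for EUC, travel and in-person attendance. These times are self-reported and valued at the regional median wage. Provider time is wider: "the number of hours worked obtained from provider maintained logs", multiplied by the provider's wage.

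The phone arms teach the same topics in different places.

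- **GP** (Group phone intervention: Delivery/session content): each 45-minute meeting includes "a lesson on a weight management topic, and an experiential learning assignment", the assignment being due before the next meeting.
- **IP** (Individual phone intervention: Delivery/session content): "Prior to each call participants will be asked to read a lesson in the study notebook". In the call of about 15 minutes, "health educators will highlight the major points of the lesson". The section concludes that "the IP intervention is predominately self-directed with minimal education and support from the health educator".
- **Both** (Intervention, General Description): the notebooks are identical and "contain handouts, worksheets, and assignments specific to each session".

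Total cost and cost per kg are compared between arms by one-way ANOVA at 6 and 18 months.

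**The concern.** The costing rule draws its line at the call, and the two phone arms put the lesson on opposite sides of that line. In GP the teaching is costed as participant time. In IP the recap by the educator is costed, but the reading that carries most of the content is not. Provider time outside calls can enter through the logs; participant time outside calls cannot.

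This bears on the GP-IP comparison in particular. Shakes, shipping and notebooks are planned alike in both phone arms, so they largely cancel in the difference in total cost, and time is a main part of what remains. Costs are to be collected prospectively, so reading time that is not asked about during the trial could later be recovered only by recall.

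**Working it through.** The plan states no participant-hours or cost figure, so there is none to reproduce.

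**Inputs from the documents.** GP calls last 45 min and IP calls about 15 min; both are weekly in months 0-6 and every two weeks in months 7-18. GP groups have 12-15 members. Hypothesised 6-month losses are 12 kg (GP) and 8 kg (IP). Two shakes a day are supplied to month 6.

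**Assumptions (not in the documents).** Reading takes r = 10-20 min per lesson. A provider hour is worth w = 1-3 participant hours. Participant wage is $15-25/h.

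**1. Scheduled time, full attendance**
- Sessions: 26 + 26 = 52.
- GP: 52 x 45/60 = 39 h. IP: 52 x 15/60 = 13 h. Gap: 26 h.

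**2. Uncounted reading per IP participant**
- r = 10: 52 x 10/60 = 8.7 h, or 33% of the gap.
- r = 20: 52 x 20/60 = 17.3 h, or 67% of the gap.
- In money: 8.67 x $15 = $130 up to 17.33 x $25 = $433.
- With half the sessions attended and half the lessons read: 4.3-8.7 h of a 13-h gap, the same shares.
- GP participants are asked to dial in about five minutes early. If that is reported as attendance, the gap becomes 26 + 52 x 5/60 = 30.3 h and the shares 29-57%.

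**3. Offset from assignments.** If GP assignments take a minutes longer than IP assignments, the net omission is 52(r - a)/60 h. With r = 10, a = 10 gives zero and a = 15 gives -4.3 h, so the direction reverses.

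**4. Total cost, call time only, in participant-minutes per session**
- GP: 45 + (45/15 to 45/12)w = 45 + (3 to 3.75)w. IP: 15 + 15w + r.
- Equal at w = (30 - r)/12 to (30 - r)/11.25.

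| r (min) | w at equal cost |
|---|---|
| 0 | 2.5-2.67 |
| 10 | 1.67-1.78 |
| 20 | 0.83-0.89 |

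- At half attendance, if group calls still run and missed IP calls are not held, the r = 0 case becomes 22.5 + (3 to 3.75)w = 7.5 + 7.5w, giving w = 15/4.5 = 3.3 to 15/3.75 = 4.0. The crossover moves with attendance, so no single value can be relied on.

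**5. Cost per kg at 6 months.** Shared costs do not cancel here, because they are divided by different weight losses. Let S be the weekly shake and shipping cost in participant-minutes, with no reading.
- (45 + 3w + S)/12 = (15 + 15w + S)/8 gives w = (180 - 4S)/156; with 3.75w, w = (180 - 4S)/150.
- At w = 1 these need S = 6 and 7.5 min, worth $1.50 (6 min at $15/h) to $3.13 (7.5 min at $25/h) a week. Over 14 shakes that is 11-22 cents each, shipping included.
- If shakes cost more than that, IP is already dearer per kg for every w from 1 to 3, and adding reading only widens its excess. The GP conference platform is unpriced and left out.

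**The case against.** The strongest objection is about direction. GP has an explicit uncosted task between meetings, and the IP section describes no equivalent. The identical notebooks suggest that both arms do assignments and that these largely cancel, but no section times either activity. This stands, and it is why the conclusion is conditional. A reader might infer that IP cost is understated without qualification; the documents do not support that.

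A reader might also infer that the omission would reverse the ranking of the phone arms. For total cost that depends on wages, attendance and assignment time that the plan does not give. For 6-month cost per kg a reversal is unlikely, as step 5 shows.

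Second, the plan has places where reading time might surface: a process flow chart meant to account for all resources, and structured interviews that ask about resource use. So it would be wrong to say that the authors chose to exclude reading. But the flow chart does not alter the participant-cost rule, and the interviews invite a 20% convenience sample, about 0.20 x 80 = 16 IP participants. Neither yields a value for each participant for the ANOVA.

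Third, any costing has a boundary. Exercise and self-monitoring time are also uncosted. Their protocols are the same in GP and IP, so they do not explain away this imbalance. The point does have force for the comparison with EUC, where prescribed activity differs (225 against 150 min/week) and would remain outside the cost.

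**Conclusion.** The concern holds in conditional form. As written, the rule costs the lesson in GP and leaves its IP counterpart uncosted, which sits badly with a societal perspective. IP participant cost is likely to be too low relative to GP, by up to 8.7-17.3 h per participant over 18 months if each lesson takes 10-20 minutes and all are read, less any extra time that GP assignments take. The size rests on an assumed reading time. The share of total cost cannot be computed, because wages, shakes, shipping, space and the conference platform are not priced. The cost-per-kg conclusion also rests on the hypothesised 12 and 8 kg losses and on shakes costing more than 11-22 cents each.

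This is a cheap improvement to a secondary analysis. The weight outcomes and the primary comparison are untouched.

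**What to change.** In Participant costs, define participant time as session attendance plus required lesson reading and assignments, with travel added for EUC. Collect it prospectively from all participants in all three arms, with the same self-report items and recall period, instead of relying on the interview subsample. Use it in the total-cost and cost-per-kg comparisons under Cost analysis, and report session-only time as a sensitivity analysis. State that exercise and self-monitoring time remain outside the cost boundary, if that is the intention.

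The cost is one or two extra self-report items at each cost collection and a revised definition. Self-reported reading time will be imprecise, which is the reason for keeping the session-only analysis. The interventions, sample size and primary analysis do not change.

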### **Recruitment/randomization**

In addition to recruitment by rural clinic personnel, we will also recruit using flyers posted in rural communities and media advertising including print, radio and Facebook®. We will recruit at least 50% females and minorities to reflect or exceed minority representation in rural Kansas (16.7%) (49). Potential participants will be asked to contact study staff via phone, email or our laboratory web site. Interested individuals will be directed to complete a brief web-based screener on our laboratory website, or will be interviewed by phone, to assess self-reported height and weight (BMI), medication use, presence of chronic disease, smoking habits, previous attempts at weight loss, and current level of PA. Those satisfying the initial eligibility criteria will be scheduled to attend an in-person meeting with study staff at the participant's respective clinic. At this session staff will describe the project, answer questions, obtain consent, complete eligibility screening surveys, and measure height and weight to determine preliminary eligibility based on BMI. Screening surveys including health history, depression, eating behavior and binge eating will be administered using web-based software (Research Electronic Data Capture software (REDCap), Vanderbilt University, Nashville, TN) (50). These surveys will be completed during the in-person meeting or at home, depending on the availability of home internet access. Project staff will then send a form (fax/email) to the potential participant's primary care physician describing the study and requesting clearance for participation. Final eligibility based on BMI will be confirmed at baseline testing, using height and fasting weight assessed with participants wearing hospital gowns. Participants in each clinic will be randomized, stratified by sex, to one of the three study arms. The randomization sequence will be generated by an independent statistician, sent to the project coordinator and concealed until intervention groups are assigned.

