### **Statistical power and analysis**

**Statistical power.** Differences in weight loss at six mos. between participants randomized to the IP or EUC, and GP or IP are of primary interest. We hypothesize that six month weight loss will average 2 kg, 8 kg, and 12 kg in the EUC, IP, and GP arms, respectively, with a common standard deviation for weight change of 7 kg (34) (35). Statistical power was determined assuming a type 1 error rate of 2.5% for each of our two primary comparisons. Based on these assumptions, randomization of 200 participants with a 2:2:1 allocation; GP (n=80), IP (n=80), EUC (n=40) will provide 98% power to detect significantly greater weight loss in IP versus EUC, and 91% power to detect significantly greater weight loss in GP versus IP. The global F-test for a one-way ANOVA provides greater than 99% power under these assumptions. The primary analysis will be intent-to-treat with imputation of missing data using multiple imputation techniques. However, a completers only analysis, with a 20% loss to follow-up, will still provide 95% power for the IP-EUC, and 83% power for the GP-IP comparisons.

**Analysis plan.** A global one-way ANOVA will be followed with two pairwise t-tests on the two comparisons of interest, IP versus EUC, and GP versus IP. Statistical significance for each pairwise comparisons will be  $p \leq 0.025$ ; however, all other analyses will be conducted at  $p < 0.05$ . These primary analyses will be intent-to-treat utilizing multiple imputation for missing data and to determine corresponding  $p$ -values. In addition to the intent-to-treat analysis, a completers only analysis will be performed, i.e., participants with weight at 6 months. Secondarily, we will compare weight between the three study arms across 24 months using a mixed linear model,

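### The total-cost ANOVA has no clinic term, although arms are randomised within clinic and part of provider cost is set by clinic, so its intervals may be too wide or too narrow

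*Combined protocol and SAP*

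**What the plan says.** Under Cost considerations, the Cost analysis paragraph reads: "Differences in total costs and cost effectiveness; i.e., cost/kg weight loss between intervention arms will be evaluated using a one-way analysis of variance (ANOVA". This point concerns total cost, not the cost-per-kilogram ratio. No clinic factor, random effect or robust standard error is named there or in Statistical power and analysis, which puts the non-primary tests at the 5% level ("however, all other analyses will be conducted at" p < 0.05). The same Cost analysis paragraph ends: "Contingent valuation data will be analyzed using conditional logit analysis, with adjustments for clustering of observations within clinics".

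Three other places matter:

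- **Provider costs.** Space is costed by "multiplying the local market values for office per square foot by the amount of space utilized". Utilities come from monthly bills, and educator time is logged hours times that provider's wage. Shake purchase and shipping come from billing records. How any shared amount is assigned to a participant is not stated.
- **Delivery.** "The GP intervention will be delivered to 12-15 participants during a 45 minute call weekly", so educator time on a group phone (GP) call is shared. Individual phone (IP) calls of about 15 minutes and enhanced usual care (EUC) meetings of about 45 minutes are one to one. One educator per clinic delivers all three arms (Health educator selection/training).
- **Randomisation.** "Participants in each clinic will be randomized, stratified by sex, to one of the three study arms". Clinic recruitment asks for 40 participants from each of at least five clinics.

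**The concern.** A one-way ANOVA treats every value as independent within its arm. Two features of this trial break that assumption for total cost, and they act in opposite directions.

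1. Arms are crossed with clinic. A clinic difference that adds the same amount in every arm cancels from the arm contrasts but stays in the ANOVA residual. Standard errors are then too large.
2. Some cost variation is specific to one arm of one clinic. GP educator time is shared by everyone on the call. One clinic wage multiplied by different hours per arm also gives different amounts in each arm. This variation does not cancel, and the ANOVA divides it by the number of participants when only about five clinics contribute independent values. Standard errors are then too small.

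The cost differences between GP, IP and EUC are a stated output at 6 and 18 months, so their intervals need to be right.

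**Working it through.** **Plan's own figure.** There is none to reproduce. The plan gives no variance, intraclass correlation or power for cost. The variance shares below are therefore assumptions, shown over a range.

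**Layout.** 40 per clinic at 2:2:1 gives 16 GP, 16 IP and 8 EUC. Five clinics give 80/80/40, matching the plan's arm sizes. Analysis of participant totals is assumed.

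**Formula.** Let total cost variance within an arm be 1, with share c for a clinic effect common to all arms and share r for clinic-by-arm. For GP minus IP:

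- True variance = (1 − c − r)(2/80) + 2r/5.
- The ANOVA uses approximately 2/80.
- Ratio = (1 − c − r) + 16r = 1 − c + 15r.

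The ratio is slightly understated, because the pooled residual does not capture all the between-clinic variance.

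- c = 0, r = 0.10: ratio 2.5, so the true standard error is √2.5 = 1.58 times the reported one.
- c = 0.50, r = 0: ratio 0.5, so the true standard error is about √0.5 = 0.71 of the reported one.
- The two effects balance when r is roughly c/15. A small clinic-by-arm share offsets a large common one.

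**Simulation.** No true cost difference, nominal 5%, 20,000 replicates per setting for the planned test:

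| Assumed clustering | One-way ANOVA rejects |
|---|---|
| None | 5.1% |
| Common clinic share 20% | about 3% |
| Common clinic share 50% | about 1% |
| Clinic-by-arm share in GP only, 10% | about 12-13% |
| Clinic-by-arm share in GP only, 20% | about 20-21% |
| Clinic-by-arm share in all arms, 5% | about 15% |
| Clinic-by-arm share in all arms, 10% | about 25% |
| Clinic-by-arm share in all arms, 20% | about 41-42% |
| Common 50% plus 2% clinic-by-arm in all arms | 4.0% |
| Common 50% plus 5% clinic-by-arm in all arms | 10.9% |

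An F-test on the 15 clinic-by-arm means with clinic as block (2 and 8 df) rejected 4.7% to 5.4% of the time in the settings with no clustering, a common clinic effect, clinic-by-arm variation in all arms, or both.

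**Is clinic-by-arm variation plausible here?** Take 26 weekly sessions in the first six months:

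- IP educator contact per participant: 26 × 0.25 h = 6.5 h.
- GP, with one call for a clinic's 16 participants: 26 × 0.75 h / 16 = 1.2 h.
- Ratio: 6.5/1.2, about 5.

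A clinic with a higher wage therefore raises IP cost about five times as much as GP cost. A simulation used this mechanism alone, with an assumed mean wage of $30/h, wage coefficient of variation 10-20% and individual cost SD $50-200. Nominal 95% intervals for IP minus GP covered between about 71% and 95%. At 20% and $100, coverage was 87%. This does not depend on the arms costing the same.

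**The case against.** A reader might infer that provider cost is largely one figure shared by everyone in a clinic's arm, so that false cost differences are likely. The documents do not support either half of that.

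- **Much of the cost is individual.** Participants order their own shakes, IP and EUC educator time can be logged per person, and participant time and mileage are self-reported. The perspective is societal. About 52 GP calls (26 weekly, then 26 biweekly) of 45 minutes take 39 h of each participant's time, against 39/15 to 39/12, or 2.6 to 3.3 h, of educator contact per head. The shared part may therefore be a small share of the variance. This stands, and it is why the GP-only rows belong beside the all-arm rows.
- **Crossing protects the test.** With arms crossed with clinic and one educator for all three, common wage and rent differences make the ANOVA conservative. This stands only where they add equal amounts in each arm. Wage times unequal hours does not.
- **Equal costs are implausible.** GP and IP have about 52 contacts plus supplied shakes, while EUC has four meetings. This stands: a false-positive rate is a poor measure of harm, and interval coverage is the better one.
- **The unit is not stated.** The plan does not say that the ANOVA uses participant totals. On the 15 clinic-by-arm means it would hold about 5% under clinic-by-arm variation and be conservative under a common clinic effect. This stands as a condition on the finding, and it shows that the unit and the allocation rule need stating.

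**Conclusion.** The concern holds in limited form. The planned test ignores the clinics within which the trial randomises, and it omits an adjustment that the same paragraph makes for other data. If run on participant totals, it gives miscalibrated standard errors for total-cost differences. Neither direction nor size is fixed by the documents. Over the assumed shares, nominal 5% rejection runs from about 1-3% (common clinic share 50-20%), through about 12-20% (10-20% clinic-by-arm share in GP only), to about 15-42% (5-20% share in all three arms). The practical consequence is unreliable intervals, not probable false positives. This is a secondary economic analysis, and the primary weight comparison is outside this point.

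**What to change.** 1. State how shared provider costs (space, utilities, GP educator time) are allocated to participants, and that the unit of analysis is total cost per participant.
2. Analyse that total with clinic as a block and a random clinic-by-arm effect, using Kenward-Roger degrees of freedom, and report arm differences with intervals from this model. A clinic main effect alone is not enough, because clinic-by-arm variation would still be unmodelled.
3. An analysis of the clinic-by-arm mean costs with clinic as block is a simple alternative, with (5 − 1) × (3 − 1) = 8 residual df for five clinics. It is approximate, not equivalent to the mixed model, because EUC cells average 8 people and the others 16.

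The change takes a sentence or two, needs no new data, and can be run in the SAS software already planned. The price is wider intervals on few degrees of freedom when clinic-by-arm variation is real.
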